Rheumatology consultation and testing ²³																
Hematology consultation, testing, and biopsy ²⁴																
Clinical Labs																
Urinalysis	X											X				
CBC with differential	X		X		X		X		X		X			X		
TSH ⁹	X		X		X		X		X		X			X		
Complete serum chemistry	X		X		X		X		X		X			X		
Amylase and lipase ⁹	X											X				
Coagulation tests	X															
Vitamin B12, folate, iron, erythropoietin, haptoglobin, and transferrin levels and reticulocyte count ²⁵																
NHL Only Procedures																
PET-CT or CT scan ¹²												X (±7 days; odd cycles only)				

	Cycle 2								Cycle 3 and Beyond							
	Week 1		Week 2		Week 3		Week 4		Week 1		Week 2		Week 3		Week 4	
	D1	D4 ±1 day	D8	D11 ±1 day	D15	D18 ±1 day	D22	D25 ±1 day	D1	D4 ±1 day	D11 ±1 day	D15	D18 ±1 day	D22	D25 ±1 day	
Visit Type	Clinic Visit	Phone Call	Clinic Visit	Phone Call	Clinic Visit	Phone Call	Clinic Visit	Phone Call	Clinic Visit	Phone Call	Phone Call	Clinic Visit	Phone Call	Phone Call	Phone Call	
Lymph node core biopsy ²									X (±7 days; C6 only)							
EORTC QLQ-C30 and FACT-Lym questionnaires ¹⁴	X								X							
Advanced Solid Malignancy Only Procedures																
CT or MRI or PET-CT ¹⁵									X (±7 days; odd cycles only)							
Tumor biopsy ²									X (±7 days; C6 only)							
EORTC QLQ-C30 ¹⁴	X								X							
Study treatment dosing in-clinic ²⁰	X		X		X		X		X				X			
PK/CCI																
Blood draws for PK analysis ¹⁶					X				X (Odd cycles only)							
CCI																
Adverse events	Continuous															
Concomitant medications	Continuous															
Telephone contact ¹⁸		X		X		X		X		X	X		X	X	X	X

Table 3: Schedule of Assessments: End-of-Treatment and Beyond (Parts A and B)

Activity/Assessment	End-of-Treatment (EoT) Visit	Safety Follow-up Call ²²	Durability of Response and Survival Follow-up ¹⁹
	≤ 14 Days Post Last Dose	30 Days Post-Last Dose	Every 3 months for 1 year after the safety follow-up call
		+ 7 days	± 7 days
Clinical Assessments			
Patient weight	X		
Vital Signs (BP, pulse, temp) ⁴	X		
Complete physical exam	X		
12-lead ECG ⁵	X		
Echocardiogram or MUGA ⁶	X		
Ophthalmic exam ⁷	X		
ECOG	X		
Rheumatology consultation and testing ²³	As clinically indicated		
Hematology consultation, testing, and biopsy ²⁴	As clinically indicated		
Clinical Labs			
Urinalysis	X		
CBC with differential	X		
TSH ⁸	X		
Complete serum chemistry	X		
Amylase and lipase ⁹	X		
Coagulation tests	X		
Serum hCG pregnancy test ¹⁰	X		

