6.2.8. KPT-9274 Dose Reduction Guidelines for Toxicity

For Grade 2 toxicities present at baseline, the drug will not be held and the treating investigator will closely monitor and support the patient.

Patients are expected to be aggressively treated to minimize the likelihood and/or severity of side effects at the discretion of the Investigator (consultation with the Karyopharm Medical Monitor is strongly encouraged), particularly GI symptoms and hematopoietic toxicities as observed in KPT-9274 animal toxicology studies. See Section [6.9.1](#) for supportive care details.

For patients who do not tolerate the protocol-specified dosing schedule, KPT-9247 dose adjustments are permitted in order to allow the patient to continue the study treatment. The criteria for dose modifications of KPT-9274 for toxicities are outlined in [Table 15](#). These changes must be recorded on the eCRF. If a patient requires a dose delay of more than 28 days (> 28 days) from the intended day of the next scheduled dose, then the patient should be discontinued from the study (in exceptional situations, if the patient is clearly benefiting from the study treatment, and in the opinion of the Investigator no safety concerns are present, after discussion with the Karyopharm Medical Monitor, the patient may remain in the study).

If, after interruption of treatment and resolution of the event, treatment is resumed at the same dose and the same toxicity reoccurs with the same severity, the next treatment re-initiation must resume at the next lower dose level, irrespective of duration. Patients who do not recover (i.e., ≤ Grade 1 or baseline) within 28 days (≤ 28 days) of discontinuation of study treatment will not be permitted to re-start study treatment and will be discontinued from the study.

In the event of a DLT (Cycle 1) during the Dose Escalation Phase the patient must discontinue KPT-9274.

In the event of any other toxicity (< Grade 3) during the Dose Escalation Phase, one of the following actions may be taken at the Investigator's discretion after consulting with the Karyopharm Medical Monitor:

- Patients can continue treatment with KPT-9274 without a dose delay or reduction.
- If the decision is made to hold KPT-9274:

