# 2.6. BASELINE MEASUREMENT

For treatment period, the baseline value is defined as the latest value prior to the first dose of study treatment.

In the case an assessment performed on the same date as the first dose, but it is impossible to determine the evaluation time relative to the time of taking the first dose, the evaluation time will be assumed to be following the protocol-defined schedule.

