# 2.7. VISIT WINDOWS

For safety data that are summarized/plotted by time points, non-missing assessments from all scheduled and unscheduled visits will be mapped to an appropriate analysis visit using a windowing scheme. Analysis visit windows are defined in Table 2-1-1, Table 2-1-2 and Table 2-1-3. If there are 2 or more assessments mapped to the same analysis visit for a patient, the assessment that is closest to the target visit day will be used for analysis. If there are 2 or more assessments mapped to the same analysis visit with the same distance from the target visit day, then the latest one is selected for the analysis.

Table 2-1-1 Visit Windows for CBC with Differential and Complete Serum Chemistry (Parts A and B)

Analysis Visit Name	Target Visit Day	Study Day Range in Window
Baseline	Day 1	Prior to or on Day 1
C1D3	Day 3	Day 2 to 5
C1D8	Day 8	Day 6 to 11
C1D15	Day 15	Day 12 to 18
C1D22	Day 22	Day 19 to 23
C1D26	Day 26	Day 24 to 27
C2D1	Day 29	Day 28 to 32
C2D8	Day 36	Day 33 to 39
C2D15	Day 43	Day 40 to 46
C2D22	Day 50	Day 47 to 53
C3D1	Day 57	Day 54 to 63
C3D15	Day 71	Day 64 to 77
C4D1	Day 85	Day 78 to 91
(every 14 days)		

NOTE: Day 1 is the date of first study treatment dose. Analysis visit and visit window may change for certain parameters depending on the data availability.

**Table 2-2-2** Visit Windows for Vital Signs (Parts A and B)

Analysis Visit Name	Target Visit Day	Study Day Range in Window
Baseline	Day 1	Prior to or on Day 1
C1D2	Day 2	Day 2
C1D3	Day 3	Day 3 to 5
C1D8	Day 8	Day 6 to 11
C1D15	Day 15	Day 12 to 18
C1D22	Day 22	Day 19 to 22
C1D24	Day 24	Day 23 to 24
C1D25	Day 25	Day 25
C1D26	Day 26	Day 26 to 27
C2D1	Day 29	Day 28 to 32
C2D8	Day 36	Day 33 to 39
C2D15	Day 43	Day 40 to 46
C2D22	Day 50	Day 47 to 53
C3D1	Day 57	Day 54 to 63
C3D15	Day 71	Day 64 to 77
C4D1	Day 85	Day 78 to 91
(every 14 days)		

NOTE: Day 1 is the date of first study treatment dose. Analysis visit and visit window may change for certain parameters depending on the data availability.

Table 2-3-3 Visit Windows for CBC with Differential, Complete Serum Chemistry Clinical Laboratory Tests and Vital Signs (Part C)

Analysis Visit Name	Target Visit Day	Study Day Range in Window	
Baseline	Day 1	Prior to or on Day 1	
C1D8	Day 8	Day 2 to 11	
C1D15	C1D15 Day 15 Day 12 to 18		
C1D22	Day 22	Day 19 to 25	
C2D1	Day 29	Day 26 to 35	
C2D15	Day 43	Day 36 to 49	
C3D1	Day 57	Day 50 to 63	
C3D15	3D15 Day 71 Day 64 to 77		
C4D1	Day 85	Day 78 to 91	
(every 14 days)			

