# **5.3.** LABORATORY SAFETY VARIABLES

#### 5.3.1. Definitions

Clinical laboratory data of interest consists of blood analysis, including hematology and serum chemistry and coagulation. Clinical laboratory values in conventional units will be converted using the international system of units (SI).

The laboratory parameters will be classified as follows:

- Hematology test will be performed at screening visit, on day 1 of every cycle, and at the EoT visit.
- Complete Serum Chemistry panel will be measured at Screening Visit on day 1 of every cycle and at the EoT visit.
- Coagulation test will be performed at screening visit and at the EoT visit.

Table 5-2 presents the clinical laboratory tests that will be analyzed.

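### The SAP 2.7 visit windows have no end-of-treatment row, so post-treatment laboratory and vital-sign values can be reported under cycle-day labels; the Baseline row also conflicts with SAP 2.6

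*SAP*

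**What the plan says.** SAP 2.7 covers data of one kind: "For safety data that are summarized/plotted by time points". For these, "non-missing assessments from all scheduled and unscheduled visits will be mapped to an appropriate analysis visit using a windowing scheme". Within a window the value nearest the target day is used. If two are equally near, "then the latest one is selected for the analysis".

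There are three window tables: CBC and chemistry in Parts A and B, vital signs in Parts A and B, and all of these for Part C. They are listed as Tables 2-1-1 to 2-1-3; the second and third carry different numbers above the tables themselves. Each has a Baseline row with target Day 1 and range "Prior to or on Day 1", followed by cycle-day rows to C4D1 and then every 14 days. None has an EoT or post-treatment row.

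The EoT visit is nevertheless scheduled. Protocol Table 3 places it at "≤ 14 Days Post Last Dose" and lists CBC, chemistry and vital signs; Table 7 does the same for Part C. The SAP knows this: "Hematology test will be performed at screening visit, on day 1 of every cycle, and at the EoT visit" (SAP 5.3.1), with parallel statements for chemistry there and for vital signs in SAP 5.4.

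On baseline, SAP 2.6 states that "the baseline value is defined as the latest value prior to the first dose of study treatment", and SAP 3.2 and the general rules of SAP 5 agree.

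By-visit output is planned. Protocol 9.8.2 summarizes values and changes from baseline at each evaluation for every laboratory parameter, and SAP 1.7 reports no change to the protocol's statistical section. SAP 5.4 plans the same for vital signs. SAP 5.3.2 allows box plots over time.

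**The concern.** A by-visit table is read as describing patients who reached that point of the schedule on study drug. If a patient stops and has an EoT visit up to two weeks later, the windows give that record a cycle-day label the patient did not reach on treatment. It then counts in the visit's n, mean and box plot beside patients still dosing.

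Every patient who stops and attends EoT produces such a record. Those who stop for toxicity are one case: "In the event of a DLT (Cycle 1) during the Dose Escalation Phase the patient must discontinue KPT-9274" (protocol 6.2.8). Anemia was reported in 32 of 47 patients (protocol Table 11) and transfusion is allowed, so a hemoglobin at EoT may reflect recovery, transfusion or continuing decline. Pooled under a cycle day, these cannot be told apart from on-schedule values.

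The Baseline row raises a separate question. Taken literally it admits a Day 1 post-dose reading and prefers it to the pre-dose one, which the SAP's own baseline definition does not allow.

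**Working it through.** The documents state no figure on this point, so the check applies the rules as written.

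**Inputs.** Windows and selection rules: SAP 2.7. EoT up to 14 days after last dose: protocol Tables 3 and 7. Dosing days 1, 3, 5, 8, 10, 12, 15, 17, 19, 22, 24 and 26 of each 28-day cycle: protocol 6.2.3. Cohorts of 3 or 6: protocol 6.2.5.

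**1. Are there gaps?** In Table 2-1-1 the ranges after baseline are Days 2–5, 6–11, 12–18, 19–23, 24–27, 28–32, 33–39, 40–46, 47–53, 54–63, 64–77 and 78–91. Each starts the day after the previous one ends. The same holds in the other two tables, so no post-treatment day falls outside a window.

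**2. Where do EoT days land?** Twelve dosing days × 3 cycles × 14 possible EoT days = 504 pairs. Nine fall after Day 91 (five for last dose Day 82, three for Day 80, one for Day 78), leaving 495. All 495 land in a cycle-day window. The window's target day is later than the last dose in:
- 443 of 495 (89%) for laboratory tests, Parts A and B;
- 444 of 495 (90%) for vital signs, Parts A and B;
- 435 of 495 (88%) for Part C.

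These count possible days. They are not expected patients.

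| Last dose | EoT day | Parts A/B label | Part C label |
|---|---|---|---|
| Day 12 | 26 | C1D26 | C2D1 |
| Day 26 | 27 | C1D26 | C2D1 |
| Day 26 | 28–32 | C2D1 | C2D1 |
| Day 26 | 33–35 | C2D8 | C2D1 |
| Day 26 | 36–39 | C2D8 | C2D15 |
| Day 26 | 40 | C2D15 | C2D15 |
| Day 54 | 55–63 | C3D1 | C3D1 |
| Day 54 | 64–68 | C3D15 | C3D15 |

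**3. Is the mapped value also the reported one?** Not always, because the value nearest target wins (laboratory examples, Parts A and B).
- Last dose Day 26, EoT Day 27: the scheduled Day 26 CBC is at distance 0 and EoT at distance 1. EoT is not used.
- Last dose Day 12, EoT Day 26: distance 0 from the C1D26 target. EoT is used.
- Last dose Day 12, unscheduled CBC Day 13, EoT Day 15: both fall in C1D15, at distances 2 and 0. EoT replaces the earlier reading.
- Last dose Day 26, EoT Day 40: distance 3 from the C2D15 target. EoT is used unless an unscheduled value lies closer.

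**4. Weight of one patient.** If all n patients of a cohort have a value at the visit, one is 1/3 = 33% or 1/6 = 17%. A DLT in 1 of 3 patients expands the cohort to 6, so 17% is usually the better figure after a DLT; 33% fits early stops for other reasons, such as progression. Replacement or dropout changes n.

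**5. Effect on a mean.** Let m be the mean of the n − 1 dosed patients and e the EoT value. The reported mean is [(n − 1)m + e]/n, which differs from m by (e − m)/n. The sign is the sign of e − m. With assumed hemoglobin changes of −3.0 and −1.0 g/dL, which the documents do not give:
- EoT recovered (m = −3.0, e = −1.0): (2 × −3.0 − 1.0)/3 = −2.33; (5 × −3.0 − 1.0)/6 = −2.67.
- EoT worse (m = −1.0, e = −3.0): (2 × −1.0 − 3.0)/3 = −1.67; (5 × −1.0 − 3.0)/6 = −1.33.

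The same rule understates the fall in the first case and overstates it in the second.

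**6. Baseline.** Take one pre-dose and one later post-dose value on Day 1. Both are at distance |1 − 1| = 0 from target, so the tie rule of SAP 2.7 picks the post-dose value. SAP 2.6 picks the pre-dose value.

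**The case against.** Several objections limit the point, and most of them stand.

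- **Treatment period.** SAP 2.4 runs it to 30 days after last dose, or to the day before new antineoplastic therapy. An EoT value within 14 days normally lies inside it. Including the value is therefore legitimate; the cycle-day label is what is wrong.
- **Held doses.** Protocol 7.5.4.1 has laboratory tests done on the scheduled day even when drug is withheld, so off-drug values at nominal days are partly by design. That concerns patients still following the visit schedule. It does not cover a separate visit timed from the last dose.
- **Every EoT value is misreported.** A reader might infer this. Step 3 shows that it is not so, because a closer scheduled value can displace the EoT value.
- **Toxicity is understated and dose choice misled.** A reader might infer this too. The documents do not fix the direction, since EoT may fall near the nadir or after recovery. Escalation rests on DLTs and on ongoing review of all AEs and laboratory abnormalities (protocol 6.2.6.1 and 6.2.6.3), not on by-visit means. DLT stops are also uncommon so far: 2 DLTs in 47 patients (protocol 1.2.1).
- **The EoT result is lost.** It is not: protocol 9.4 provides by-patient listings of all eCRF data.
- **A post-dose value will become baseline.** Three SAP sections say otherwise. C1D1 laboratory tests are scheduled pre-dose, and vital signs pre-dose if possible (protocol 7.5.1.2). The planned 4-hour post-dose ECG on C1D1 is outside the window tables. What remains is a conflict of wording, with no statement of which text governs the Baseline analysis visit.
- **Windows may change.** The note under each table lets them vary with data availability, but it gives no rule for EoT.

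**Conclusion.** The point holds as a defect in the labelling and pooling of by-visit safety data. Followed exactly, SAP 2.7 places EoT and later unscheduled CBC, chemistry and vital-sign values in cycle-day windows. Where no value lies closer to target, it reports them there alongside patients still dosing. One such patient carries 33% of a visit in a cohort of 3 and 17% in a cohort of 6, assuming all cohort members have a value at that visit. The sign of the distortion depends on recovery and cannot be stated in advance; the hemoglobin figures above are assumed and only show that it can go either way.

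The affected outputs are the by-visit laboratory summaries (protocol 9.8.2), the by-visit vital-sign summaries (SAP 5.4) and any box plots over time (SAP 5.3.2). DLT, MTD, worst-grade and shift-table results and the listings do not depend on the windows.

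The Baseline row is a true internal conflict with SAP 2.6, 3.2 and 5. Its practical exposure is small: it needs an unscheduled or late post-dose CBC, chemistry or vital-sign value on Day 1.

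**What to change.** In all three window tables, add an analysis visit named EoT/post-treatment. State in SAP 2.7 that records from the EoT visit and later go to it and not to a cycle-day window. Change the Baseline row to the last value before first dose, with a reference to Section 2.6.

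The cost is a table edit and minor programming. Some cycle-day visits will have slightly fewer values, because patients who have stopped no longer contribute to them; their results appear in the new row.

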# 2.8. SUBGROUPS

No subgroup analysis is planned due to the small sample size.

# 2.9. POOLING OF CENTERS FOR STATISTICAL ANALYSES

All participating centers in the study will be pooled together for analysis.

# 2.10. COMPUTING AND CODING STANDARDS

Activities will be performed using the following tools:

Table, listing, and figure production	SAS Version 9.4 or higher	
Coding		
AEs	MedDRA Version 23.1 or higher	
Medical Histories	MedDRA Version 23.1 or higher	
Prior and Concomitant Medications	WHO DDE Version September 2020 or higher	

Grading	
AEs	CTCAE Version 4.03 or higher
Labs	CTCAE Version 4.03 or higher

# 3. PATIENT INFORMATION

# 3.1. DISPOSITION OF PATIENTS AND ANALYSIS POPULATIONS

Patient disposition will be summarized in each of the following categories:

- Patients who were enrolled
- Patients who received at least one dose of the study treatment (partial or complete)
- End of treatment:
  - o Patients who discontinued treatment and primary reason for discontinuation
- Survival follow-up status
  - o Patients willing to continue in Survival Follow-up
- End of study
  - o Patients who withdrew from study and primary reason for study withdrawal

A by-patient listing of study completion information, including the reason for study withdrawal may also be provided.

# 3.1.1. Efficacy Populations

# **Modified Intent-to-Treat Population**

The modified intent to treat (mITT) population for Part A, Part B, and Part C will consist of all patients who receive at least one dose of study treatment.

mITT population will be used for primary analyses of efficacy.

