9. STATISTICAL METHODS

A statistical analysis plan (SAP) will be finalized prior to database lock. Any changes from the statistical analyses described in this document will be described in the SAP, and any deviation from the final SAP will be described in the final report.

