9.3. Analysis Populations

9.3.1. Intent-to-Treat Population

The intent to treat (ITT) population for Part A and Part B will consist of all patients who receive at least one dose of the RP2D \pm niacin ER chosen for expansion. Note that patients who are in the Dose Escalation Phase being treated at the RP2D \pm niacin ER dose will be included.

The ITT population for Part C will consist of all patients who receive at least one dose of study treatment.

ITT population will be used for primary analyses of efficacy.

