9.3.2. Per Protocol Population

The per-protocol (PP) population will consist of all ITT patients who have received at least 2 cycles of study treatment, are compliant with study assessments, have received at least 80% of their prescribed study medication, and have no major protocol violations that would compromise the assessment of efficacy. Major violations will be determined independently of knowledge of response to therapy, and prior to database lock and study analysis. This population will be used for supportive inferences concerning efficacy, however, if there are major differences between the results in this population and those obtained in the mITT population, this will be taken into consideration in the assessment of efficacy.

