# Dose Expansion

- To evaluate the safety and tolerability of the RP2D and schedule(s) for KPT-9274 ± niacin ER.
- To determine preliminary evidence of anti-tumor activity of KPT-9274 at the RP2D ± niacin ER in patients with advanced solid malignancies or NHL according to Response Evaluation Criteria in Solid Tumors, Version 1.1 or Lugano Classification, respectively.

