# 1.7. MODIFICATIONS TO THE STATISTICAL SECTION OF THE PROTOCOL

The current SAP is based on Protocol Version 5.0 dated 1 March 2020. No modifications were made to the statistical section of the protocol.

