# Efficacy evaluable (EE) Population

The efficacy evaluable (EE) population will consist patients who have received at least one post-baseline disease response assessment. This population will be used for supportive inferences for primary analyses of efficacy.

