# Per-protocol (PP) Population

The per-protocol (PP) population will consist of all patients who have received at least 2 cycles of study treatment, are compliant with study assessments, have received at least 80% of their prescribed study treatment, and have no major protocol violations that would compromise the assessment of efficacy. Major violations will be determined independently of knowledge of response to therapy, and prior to database lock and study analysis. This population will be used for supportive inferences concerning efficacy, however, if there are major differences between the results in this population and those obtained in the mITT population, this will be taken into consideration in the assessment of efficacy.

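### The SAP replaces the protocol's RP2D-based primary efficacy set for Parts A and B with all treated patients, declares no change, and gives the RP2D expansion objective no analysis population

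*SAP*

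**What the plan says.** Protocol 9.3.1 gives this definition: "intent to treat (ITT) population for Part A and Part B will consist of all patients who receive at least one dose of the RP2D". The RP2D meant is the one chosen for expansion, with or without niacin ER. The section notes that escalation patients treated at that dose are included, and it names this set for the primary efficacy analyses. Only Part C uses all treated patients. Protocol 9.3.2 nests the per-protocol (PP) set in it: the PP "population will consist of all ITT patients who have received at least 2 cycles of study treatment" and meet further compliance conditions.

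SAP 3.1.1 names a modified intent-to-treat set for the same primary use. That "population for Part A, Part B, and Part C will consist of all patients who receive at least one dose of study treatment". The PP "population will consist of all patients who have received at least 2 cycles of study treatment", with no mention of ITT. An efficacy-evaluable (EE) set, absent from protocol 9.3, is added; this "population will consist patients who have received at least one post-baseline disease response assessment".

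On changes, protocol section 9 says: "Any changes from the statistical analyses described in this document will be described in the SAP". SAP 1.7 says: "No modifications were made to the statistical section of the protocol".

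The SAP keeps the RP2D question. One primary Dose Expansion objective in SAP 1.2.1 is "To determine preliminary evidence of anti-tumor activity of KPT-9274 at the RP2D", with or without niacin ER. SAP 1.1 (Dose Expansion Phase), like protocol 9.1, still places escalation patients treated at the chosen dose in the expansion efficacy analysis.

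**The concern.** Two things are wrong.

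The first is disclosure. The primary efficacy set for Parts A and B, the PP set and the list of populations all differ from the protocol, and the SAP section meant to record such differences reports none. A reader who relies on SAP 1.7 would take the reported efficacy set to be the protocol's. This holds whether or not expansion takes place.

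The second is that an objective has no population. Activity at the RP2D is a primary expansion objective, and the rule for which escalation patients join that analysis appears in the SAP's design text. Neither reaches SAP 3.1, which is where programming specifications start. The set labelled primary for efficacy is the all-treated one. If it were used undivided for the RP2D objective, ORR, DCR and PFS would describe a mixture of the RP2D and every other dose given in that part.

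**Working it through.** **Definitions side by side**

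| Item | Protocol | SAP |
|---|---|---|
| Primary efficacy set, Parts A and B | At least one dose of the RP2D chosen for expansion (9.3.1) | All treated (3.1.1) |
| Primary efficacy set, Part C | All treated (9.3.1) | All treated (3.1.1) |
| PP set | Within ITT (9.3.2) | No ITT or RP2D condition (3.1.1) |
| EE set | None | Added, supportive (3.1.1) |
| Declared changes | Must be described in the SAP (9) | None (1.7) |

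**Does anything else in the SAP recover the RP2D set?** The populations in SAP 3.1 are mITT, EE, PP, safety and DLT-evaluable. None mentions the RP2D. SAP 2.8 plans no subgroups. SAP 4.2 names no RP2D set and refers to a treatment arm that it does not define. Output by part and cohort is specified in SAP section 5, for safety only. Table 4-1 lists every efficacy endpoint as secondary, whereas the protocol synopsis also lists them as primary endpoints for expansion.

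**The plan's own count.** Protocol 9.2.1 assumes 9 dose levels in each of Parts A and B and up to 65 expansion patients, and estimates 175 in total. With 6 per cohort, 2 × 9 × 6 + 65 = 173, which agrees with the rounded 175. With 3 per cohort, 2 × 9 × 3 + 65 = 119. The 9-level, 6-patient layout is therefore the plan's own basis.

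**Illustration of the difference within one part.** The documents give no RP2D. Assumptions: 9 levels of 3 or 6 patients, an RP2D cohort of 6, all 45 expansion patients in that part, and no dose reductions.

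- Patients at the RP2D: 6 + 45 = 51.
- Other escalation patients: 8 × 3 = 24, or 8 × 6 = 48.
- Non-RP2D share of mITT: 24/(51 + 24) = 24/75 = 32.0%, or 48/(51 + 48) = 48/99 = 48.5%.

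**Effect on an estimate.** Suppose 10 of the 51 RP2D patients respond: 19.6%, exact 95% CI 9.8 to 33.1%. With x responders among the other 48, the mITT estimate is (10 + x)/99:

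- x = 0: 10/99 = 10.1% (5.0 to 17.8%)
- x = 2: 12/99 = 12.1% (6.4 to 20.2%)
- x = 10: 20/99 = 20.2% (12.8 to 29.5%)

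The mITT figure exceeds 10/51 once x > 48 × 10/51 = 9.4, that is, from x = 10 upward. The estimate can move either way.

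**The case against.** The best defence is that the SAP may be repairing a gap in the protocol. Anti-tumor activity in escalation is a secondary objective, and the protocol's RP2D set would leave most escalation patients out of any defined efficacy set. As of 02 March 2019 no MTD had been reached (protocol 1.2.1), and expansion is optional. If no dose is chosen for expansion, the protocol's set has no members. Protocol 9.3.2 itself refers to an mITT population without defining it, and Table 4-1's secondary label fits the escalation objective. All of this stands as a reason to have an all-treated set. It does not justify dropping the RP2D set while keeping the RP2D objective, and it does not make SAP 1.7 correct.

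A second defence is that SAP 1.1 already says which escalation patients join the expansion analysis, and all of them are inside mITT, so the analysis could be produced as a separate display. That is true, and it limits the point. The rule has not vanished from the SAP; it is missing from the populations and methods sections, which do not refer back to it.

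A reader might infer more than the documents support:

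- That the SAP pools doses to estimate activity at the RP2D. It does not say so; the mixing depends on how mITT is used.
- That 48% is a ceiling. It is not. With a 20-patient expansion in place of 45, the 6-per-cohort case gives 48/(6 + 48 + 20) = 48/74 = 65%. Dose reductions would work the other way, because protocol 9.3.1 counts anyone with at least one dose of the RP2D.
- That the change biases the results in a known direction. Nothing in the documents fixes the response rate at other doses.

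**Conclusion.** The point holds, and should be fixed. That the definitions differ and that SAP 1.7 is wrong follows from the text, with no assumptions. The effect on results is conditional: expansion must be conducted, and mITT must be used undivided for the RP2D objective. In that case ORR, DCR and PFS would mix RP2D and other doses, with bias of unknown direction. The 32% to 48% share is one illustration resting on the assumptions stated with it, not a general bound. The efficacy analyses are descriptive. The MTD, the futility rule and Part C are unaffected.

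**What to change.** 1. Correct SAP 1.7 to list three changes from protocol section 9: ITT to all-treated mITT for Parts A and B, the PP set no longer nested in ITT, and the added EE set.
2. In SAP 3.1.1, add the set from protocol 9.3.1, with the inclusion rule already in SAP 1.1, as the primary efficacy set for the Dose Expansion objective. State that it applies if expansion is conducted, and nest a PP set in it.
3. Keep the all-treated mITT set for the Dose Escalation secondary objective.

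This costs SAP wording and one population flag, with no new data. The statistical price is a smaller denominator and a wider interval for the expansion analysis. At a response rate near 20%, 10/51 gives an exact 95% CI of 9.8 to 33.1% (23.3 points wide), against 12.8 to 29.5% (16.7 points) for 20/99. The narrower interval answers a different question.
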